#### **10. HUMAN SUBJECTS**

This project will recruit 75 and test a total of 60 healthy elderly subjects from UCSD ADRC. We aim to test 60 participants (20 per group, 3 groups) from UCSD.

Patients who are elderly and cognitively intact will be identified, screened, and recruited from UCSD ADRC following the procedures outlined in Section 11 below.

Study testing visits will take place at SOM Building 4.

Along with the referring physician, [name] will oversee determination of whether potential subjects fit eligibility criteria according to the criteria outlined below.

**Inclusion criteria:**

- 1) Cognitively intact;
- 2) Able to give informed consent in English;
- 3) Medical clearance by their doctor;
- 4) > 60 years of age.

**Exclusion criteria:**

- 1) Alzheimer's Disease or other neurodegenerative disease such as Parkinson's Disease;
- 2) Current use or use in the past 3 months of antimicrobial or steroid drugs;
- 3) Medical conditions affecting immune status (e.g., rheumatoid arthritis, heart failure, hepatitis C, HIV);
- 4) Individuals diagnosed with Diabetes Mellitus
- 5) International travel in past 3 months.
- 6) Previous known side effect or negative reaction to VSL#3 or *Triphala*

Obtained research material will include vital signs, peripheral blood and plasma (processed and stored in Core Laboratory until assay), stool, and psychological and health behavior questionnaires.

All data will be obtained from recruited subjects for research purposes only. Data will be collected specifically for the proposed research project.

**Inclusion of Women and Minorities**

In the general population, inflammmaging and immunosenescence is not gender-specific and we will recruit both men and women for this project.

Race/Ethnicity will be studied in a relative proportion to the ethnic composition of the San Diego area. San Diego has a diverse ethnic population. We will study English-speaking Hispanic and Latino as well as non-Hispanic and non-Latino participants.

**11. RECRUITMENT AND PROCEDURES PREPARATORY TO RESEARCH**

**Overview.** A total of 75 participants who are generally healthy and otherwise meet our study criteria will be recruited and randomly assigned to either an 8-week synbiotic group, herb alone, or placebo control with a goal to obtain 60 patients who complete the study (20 in each group) after an estimated 20% attrition. Placebo control subjects will be given the option of having the 8-weeks of herbal synbiotic for directed personal use upon conclusion of the study. [name] has volunteered to help identify individuals who meet criteria for this study. Additional staff members responsible for assisting with recruitment are listed elsewhere in this application.

With this application, we are requesting a Waiver of Documented Consent to conduct the telephone screens. Asking interested individuals whether they meet the basic study criteria over the telephone (age, immune disorder diagnosis, medication use) presents no more than minimal risk of harm and involves no procedures for which written consent is normally required outside of the research context. Written consent will be obtained at the initial, in-person visit before any study questionnaires are administered or research procedures are performed.

With this application, we are also requesting a partial waiver of HIPAA authorization so that our study staff may help clinical staff identify potentially eligible participants using EPIC. When a member of our research team identifies a patient who may be eligible, he or she will then send a secure EPIC email asking the provider if they agree that a given patient is a good candidate for the study and asking the provider to speak with his or her patient about our study. The provider will provide a brief overview of the study during the patient's clinical

visit. The provider will additionally ask the patient if they would like a follow-up phone call from study staff to learn more details about the research study and see if they qualify (i.e., Telephone Screen). If the patient verbally assents, the provider will reply to the study staff via a secure EPIC email indicating that the patient is willing to be called about the study and study staff will then call the patient—only with their verbal permission. If the patient is not willing to be contacted, the provider will also indicate that via secure EPIC email, so that uninterested patients are not contacted by study staff. Using this secure communication method, there is minimal risk that any PHI could be lost or disclosed outside the designated research staff and University. All individuals with access to the PHI have been trained in privacy procedures. The PHI will remain at UCSD, and all the University and Privacy and Data Security rules will be followed. Participation in research is entirely voluntary. Interested volunteers may refuse to participate in the phone screen or opt out at any time without penalty or loss of benefits to which they are entitled at UCSD. The project could not practicably be conducted without a waiver because without a partial waiver of consent we would fail to confirm the most basic eligibility criteria (age, English-speaking, not taking antimicrobial or steroidal medication, etc.). It would not be feasible to obtain full consent and authorization from each patient in order to determine the much smaller group of patients that would ultimately meet study inclusion/exclusion criteria. Once we have identified via phone screen this smaller group who are likely eligible, it will be the patients interested in our research who will be consented for the study.

We hereby, then, request with this application a HIPAA waiver to prescreen using eMR records and a waiver of documented consent for phone screening. The research presents no more than minimal risk of harm to subjects and involves no procedures for which written consent is normally required outside of the research context.

- a. This prescreening involves minimal risk because we will utilize the eMR records to identify potential subjects. EPIC will be viewed only by authorized personnel who have completed all necessary privacy training courses. PHI will not be shared or disclosed for any other purposes;
- b. The waiver or alteration will not adversely affect the rights and welfare of the subjects because potential research subjects who are informed about the study by authorized study staff have no obligation to participate, or even be further screened for the study;
- c. The research could not practicably be carried out without the waiver because there are hundreds of new and potentially eligible patients seen annually at UCSD and it would not be feasible to obtain full consent and HIPAA authorization from each patient in order to determine the much smaller group of patients that would be eligible for the study. Once we have identified this smaller group, it will be the patients interested in our research who will be consented for the study; and
- d. The subjects will be provided with additional pertinent information after being identified as potentially eligible such as (a) the opportunity to read the ICF prior to deciding whether or not to participate (b) the opportunity to speak with authorized study staff about what participation would entail, including the study's risks and benefits, and (c) an opportunity to read and ask questions about the Research Subject's Bill of Rights.

All identifiers will be protected in accordance with University policies. These include:

1. The particular SI that will be used in this study will be clinical information in the patient's medical record file, including demographic information, laboratory tests, echocardiogram results, medication lists, problem lists, clinic notes, and other medical records.
2. All SI described will be used according to the study protocol, i.e. to determine the clinical characteristics of patients and clinical outcomes over time.
3. Only the PIs of the study, designated and approved study personnel as indicated in the protocol will have access to the SI. No person outside of the authorized study personnel will have access to the SI.
4. In the event of a real or suspected breach of security, University officials will be notified as soon as possible.

The project could not practicably be conducted without a waiver because without a partial waiver of HIPAA and consent, potentially eligible patients could not be efficiently identified due to the fact that there are hundreds of potentially eligible patients seen annually. It would not be feasible to obtain full consent and authorization from each patient in order to determine the much smaller group of patients that would ultimately meet study inclusion/exclusion criteria. Once we have identified via prescreening this smaller group who are potentially eligible, it will be the patients interested in our research who will be consented for the study. As an example, because we are looking for individuals who are over the age of 60, who have not been diagnosed with a disorder affecting their immune system, and who are not taking antimicrobial or steroid medication, it would be extremely inefficient to approach and consent individuals who do not meet at least these basic inclusion criterion.

The project could not practicably be conducted without use of PHI because EPIC uses MRNs, name and birth date to identify patients. Without having access to this PHI, we cannot review medical records. PHI to be used for prescreening would be: name, MRN, demographic data, medical record data, including clinical data related to medical conditions, medication list, and problem list.

In addition to recruiting new study patients from the ADRC, we will also conduct a retrospective review of our previous research participants who have indicated on ICFs for other studies that they are willing to be contacted for future research studies. For these participants, we are also requesting a partial HIPAA and consent waiver for prescreening purposes only to review the eMR to ensure they appear to meet our basic inclusion/exclusion criteria before contacting the patient, in an effort not to squander the study staff or patient's resources, namely time. When contacting individuals who participated in our previous studies and agreed to be contacted, we will follow the submitted telephone script.

## **12. INFORMED CONSENT**

Informed consent will be obtained by the PI or one of his trained staff-members prior to participant enrollment or any study procedures. The consent procedures will involve a thorough explanation of the study and associated procedures, as well as a review of the ICF on a point-by-point basis in a private office at UCSD. All consent is voluntary; records are kept confidential and coded by identifying participant numbers in the computer database, which requires authorized study staff to use their Active Directory login to access the password protected files. Participants will receive a copy of the ICF that they have signed and originals will be maintained by the study coordinator in a locked file cabinet.

We are requesting a Waiver of Documented consent for conducting telephone screens with potentially eligible candidates who have discussed the study with their clinical provider. If their clinical provider ascertains that the patient would like to learn more about the study and the patient verbally assents to receiving a phone call from study staff, the provider will send a secure EPIC reply to the research staff indicating such, and study staff will contact the patient by phone to explain the study and conduct the telephone screen. We are requesting that research staff be permitted to verify basic inclusion and exclusion criteria prior to the laboratory testing visit, such as inquiring whether the potential participant is over the age of 60 and does not have (a) Alzheimer's Disease or other neurodegenerative disease such as Parkinson's Disease; (b) Current use or use in the past 3 months of antimicrobial or steroid drugs; (c) Medical conditions affecting immune status (e.g., rheumatoid arthritis, hepatitis C, HIV); (d) International travel in past 3 months; (e) Previous known side effect or negative reaction to VSL#3 or *Triphala*. At the end of the call, the research assistant will schedule the interested and preliminarily eligible individual for initial study visit. This phone screening presents no more than minimal risk of harm to subjects and involves no procedures for which written consent is normally required outside of the research context. The written informed consent process will occur at the beginning of the initial in-person session and thus, the research assistant will obtain a written informed consent prior to any further data collection.

If an individual does not pass the screening, he or she will be thanked for their interest. If they do pass the screening, they will be scheduled for their initial study visit. At this in-person visit, the patient will review the ICF with the research staff and provide written informed consent to participate in the study. Once the potential

participant has been informed s/he is eligible there will be discussion about the research, risks/benefits, and alternatives to the study. If the participant wishes to delay the treatment initiation for 1 week after consent to consider alternatives, that will be permitted. The option of a week delay should remove undue influence..

### **13. ALTERNATIVES TO STUDY PARTICIPATION**

The alternative to participation is not to participate in this study. Participation is entirely optional and has no bearing on other rights to which a patient is entitled at UCSD or UCSD ADRC.

### **14. POTENTIAL RISKS**

Participation in this study may involve some added risks or discomforts. These include:

- a. Pain, risk of fainting, lightheadedness and dizziness associated with the blood draw.
- c. Mild soreness and/or a bruise at the needle site.
- d. A small risk also exists that the vein may form a clot at the needle stick, which will gradually clear over one to two weeks.
- e. Risk of local infection at blood draw site.
- f. There is risk of loss of confidentiality. This will be minimized by using an identifier number rather than patient's name on all of the information gathered for the study.
- g. There may be mild psychological discomfort answering personal questions.
- h. There may be mild psychological discomfort providing a stool sample.
- i. There is an additional risk of bleeding for people taking blood thinning medications. Though considered to be a low risk, participants may want to discuss this with their physician prior to enrolling in the study.

Since this is an experimental treatment, there may be some unknown risks that are currently unforeseeable.

There are no known drug interactions or medical risks known with taking *Triphala*; a side effect of *Triphala* includes potential slightly looser bowel movement that is transient or resolves upon reduction of dose or cessation of *Triphala*. VSL#3 may cause a side effect of possible mild abdominal bloating in the first few days of consumption, which is a transitory phenomenon due to changing intestinal microflora that is self-resolving or can be reduced by decreasing the daily probiotic dose.

### **15. RISK MANAGEMENT PROCEDURES AND ADEQUACY OF RESOURCES**

Healthy elderly subjects will be recruited at UCSD ADRC and be under the care of their physician.

The protocol will be approved by the IRB. All of the investigators and study staff have completed the federal human subjects certification.

Written consent will be obtained from each subject to review available medical records. We will make every effort to minimize the potential risks from the blood or stool sampling and the behavioral and psychosocial testing.

Subjects will be assigned an identification number, which will be used for data analysis purposes. The PI and Project Manager will have the link between the subject number and the subject's name. This information will be locked in a filing cabinet in the Project Manager's office.

Questionnaires will be labeled with subject numbers and locked in a filing cabinet in the Project Manager's office. Research records will be maintained in confidence and released only upon written consent of the subject, or as required by law.

All data analyses will be performed on aggregate data without identifiers for individual subjects. All study data will be kept confidential.

Each eligible subject's physician will be mailed a letter informing them of their patient's interest in participation in the study. Once enrolled into the study, all patients will continue to receive their usual health care from their doctors.

## **Data Safety Monitoring Plan**

This is a low risk protocol. At the request of the IRB, the study investigators have appointed [name], Professor of Medicine, as the Data Safety Monitoring Officer (DSMO) who will help ensure adequate progress, patient's safety and confidentiality of personal information. [name] is not otherwise connected with the proposed project, however his research interests are similar to those included in the present study and he has been involved in similar types of studies. [name] will be in charge of evaluating and monitoring aspects of the study including participants' physical/medical safety, side effects and adverse events. [name] is familiar with the herbs, study operations, and data collection procedures found in the present study. The DSMO will monitor participants per the following:

1. Review and assessment of the performance of the study operations.
2. Examination of interim results of the study for evidence of efficacy or adverse effects.
3. Possible termination of the study because of early attainment of study objectives.
4. Identifying safety concerns or inadequate performance by staff.
5. Ensuring that any paper records, which reflect electronic data or relationships of those data, are kept in locked cabinets. Each PC workstation's operating system has a password protection scheme that allows startup of the system only by those with knowledge of the designated password.
6. The PIs will be charged with the reporting of all deaths and serious adverse events to both the DSMO and the IRB. This notification is submitted in writing to the IRB within 24 hours. Other adverse events will be reported within 10 working days.
7. Each participant's health status will be monitored and reported by the Project Coordinator to the Safety Monitoring Board on a monthly basis. Formal Safety Monitoring Board reports will be submitted to the IRB with each continuing review application during the active phase of the project.
8. Review any adverse events if any occur. PI will ask the Project Coordinator to break the code and have the statistician in our study determine if adverse events occur significantly more frequently in any one condition.

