**5. LAY LANGUAGE SUMMARY OR SYNOPSIS (no more than one paragraph)**

Normal aging can lead to loss of gut microbial biodiversity which is linked to inflammaging and immunosenescence or the loss of immunocompetence. Probiotics, such as VSL#3®, and certain herbal supplements such as *Triphala* are associated with restoration of gut community architecture, increased gut barrier function and decreased inflammation. The present project will examine the potential benefits of a synbiotic (which denotes a prebiotic plus probiotic, and in this study, is an herbal prebiotic plus probiotic) intervention (8 weeks of supplementation) on gut microbiome profiles assessed via stool, inflammatory blood markers, and questionnaires about gastrointestinal health and mood. In this exploratory study, we will examine psychological and physical functioning at baseline and after 8 weeks of supplementation with synbiotic, *Triphala* alone, or placebo.

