**Exclusion criteria:**

- 1) Alzheimer's Disease or other neurodegenerative disease such as Parkinson's Disease;
- 2) Current use or use in the past 3 months of antimicrobial or steroid drugs;
- 3) Medical conditions affecting immune status (e.g., heart failure, inflammatory bowel disease, hepatitis C, HIV);
- 4) International travel in the past 3 months.
- 5) Previous known side effect or negative reaction to VSL#3 or *Triphala*.

Note that heart failure, inflammatory bowel disease, hepatitis C, and HIV patients are excluded due to these diseases featuring variable and significantly altered immune status and gut microbiome, which are the main outcome measures of the study. This pilot study seeks to identify relatively healthy elderly subjects to assess these markers in the context of dietary supplementation.

**Assessment visits.** Assessment personnel will be naive to the participant group assignment. Testing will take place at SOM Building 4. At T1 (baseline): participants will 1) review their study responsibilities with the opportunity to reconsider participation 2) provide a stool and small blood sample for biomarker assessment; 3) complete psychosocial measurements via questionnaires; 4) receive group assignment instructions at the end of the visit. Measures will be repeated at T2 (post-intervention period).

**Randomization.** A computer-generated randomization algorithm will determine group assignment to ensure that participant demographics are evenly distributed across study conditions.

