#### Additional Measures

Age, gender, socio-economic status, ethnic group, relationship status, education, body-mass Index and waist-hip circumference will be recorded. If for medical reasons subjects alter medications, it will be recorded via a monthly tracking form that the subject can submit.

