## **20. COMPENSATION FOR PARTICIPATION**

Participants will receive \$25 after the first and second laboratory testing sessions (T1 & T2) for a possible total of \$50 for completing the 2 testing sessions.

UCSD will provide necessary medical treatment should a subject be injured by participation in this research.

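### The safety plan promises monthly health reports on everyone and an arm comparison of adverse events, but describes no uniform way of asking participants about symptoms

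*Combined protocol and SAP*

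**What the plan says.** **Promise.** Section 15, Data Safety Monitoring Plan, item 7: "Each participant's health status will be monitored and reported by the Project Coordinator to the Safety Monitoring Board on a monthly basis". Item 8 provides for breaking the code so that the study statistician can judge whether adverse events are more frequent in one condition than in another. It names no test, significance level or data source.

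**Scheduled contacts.** Section 9 (Assessment visits) has a baseline session, T1, and then "Measures will be repeated at T2 (post-intervention period"). Section 5 places the second assessment after 8 weeks of supplementation.

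**What is collected.** Section 10: "Obtained research material will include vital signs, peripheral blood and plasma (processed and stored in Core Laboratory until assay), stool, and psychological and health behavior" (the last item being self-report instruments). Neither this list nor the measures described in Section 9 include an adverse-event form or checklist. Exploratory Aim 1 in Section 6 refers to gastrointestinal health by questionnaire, but the instruments in Section 9 do not include one.

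**Between visits.** Section 9 (Additional Measures): "If for medical reasons subjects alter medications, it will be recorded via a monthly tracking form that the subject can submit".

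**Expected effects.** Section 14 names, for VSL#3, "possible mild abdominal bloating in the first few days of consumption". For *Triphala* it names slightly looser stools of a transient kind.

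**Recipient.** Item 7 reports to a Safety Monitoring Board. The only appointment described in the same plan is a single Data Safety Monitoring Officer.

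**The concern.** A monthly report on every participant and a comparison of event frequency between arms both need the same question put to everyone at the same times. The protocol commits to both uses without describing such a question. The one form available between visits is triggered by a change of medication, so a participant with a few days of bloating and no change of medication would have nothing to report on it.

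The study has an 8-week course, and the named bloating falls at its start. If nobody asks until T2, or at all, these symptoms are recorded only when someone volunteers them. Analysts cannot later recover symptoms that were never asked about. The pilot is meant to inform a larger trial, so a tolerability statement resting on unsystematic reports would carry forward.

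**Working it through.** **1. Possible sources, set side by side.** Item 7 needs a source that reaches every participant, recurs monthly, and asks about symptoms.

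| Source in the protocol | Every participant? | Between T1 and T2? | Asks about symptoms? |
|---|---|---|---|
| T1 and T2 measures (Sections 9, 10) | yes | no | no adverse-event question listed |
| Monthly tracking form (Section 9, Additional Measures) | open to all | yes | no, medication changes only |
| Item 6 reporting of serious and other events (Section 15) | only where an event is known | yes | no, it governs reporting once known |
| Exit interviews (Section 9, Assessment Outcomes) | drop-outs only | possibly | reasons for drop-out |
| Medical-record review (Section 15) | consent from all | no schedule given | no, and mild self-limiting symptoms are unlikely to be recorded |

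No row meets all three needs.

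**2. Timing.** The course is 8 weeks. A symptom in the first few days of week 1 is more than 7 weeks old at T2.

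**3. Effect of incomplete capture on the comparison.** Let p1 and p0 be the true event rates and c the fraction of events captured, assumed equal in all arms. The expected observed difference is c·p1 − c·p0 = c·(p1 − p0), so it shrinks in proportion to c. With 40% v 10% and c = 0.5, for example, it is 0.5 × 30 = 15 percentage points.

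**4. Illustration of size.** The plan has no power figure for adverse events to reproduce, and it gives neither event rates nor capture fractions. Those are assumptions here. The other inputs are:
- n = 20 per arm, the completers in Section 10. All-recruited would be 75/3 = 25.
- Exact two-sided Fisher test at 5% (assumed, since item 8 names no test).
- Power is the sum, over all pairs of counts (i, j) with Fisher p ≤ 0.05, of Bin(i; n, c·p1) × Bin(j; n, c·p0).

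Results, 20 per arm:

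| Assumed true rates | c = 100% | 70% | 50% | 30% |
|---|---|---|---|---|
| 40% v 5% | 72% | 47% | 25% | 6% |
| 40% v 10% | 49% | 30% | 17% | 5% |
| 30% v 5% | 45% | 24% | 11% | 2% |

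At 25 per arm the 40% v 5% row becomes 82%, 56%, 28% and 6%, and the 40% v 10% row becomes 59%, 38%, 20% and 4%.

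**5. Reading.** Two limits act together. Incomplete capture cuts power in every row. Sample size alone already keeps it between 45% and 72% at 20 per arm with full capture, so better collection removes the first limit but not the second.

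**The case against.** The strongest reply is that item 7 is itself a commitment to between-visit monitoring by a named role, and that an unstated method is not proof of a passive one. Staff may telephone participants each month. The written and verbal instructions given to all arms, and the consent pages, are not in the text available for review and may cover side-effect reporting. The phrase "it will be recorded via a monthly tracking form that the subject can submit" may describe how the form is returned rather than make it optional. Safety is not a stated aim, the plan calls the study low risk, and item 8 applies only if events occur.

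Much of this stands. It rules out three stronger readings that a reader might infer:
- **That the medication form is the only channel.** Item 6 reporting, exit interviews and record access also exist. It is only the sole scheduled between-visit instrument open to all.
- **That the counts are in fact volunteered reports.** The documents do not say how the trial was conducted.
- **That a problem in the first month could reach the safety officer only at T2.** Item 6 requires serious events to be reported to the officer and the IRB, with written notice to the IRB within 24 hours. It sets 10 working days for other adverse events. A participant may also report on any day.

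Differential under-counting between arms is possible if participants guess their allocation, but nothing in the documents shows it and the illustration assumes equal capture.

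The reply does not supply the missing source. Item 6 acts on events already known and does not find them. A low-risk label does not replace asking, because Section 14 itself allows for unforeseen risks.

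**Conclusion.** The point holds as a gap between a commitment and its data source. Items 7 and 8 rely on health-status and adverse-event data from every participant, and the protocol describes no instrument that asks all of them about symptoms, whether during the 8 weeks or at T2. Under-capture of mild early symptoms, and an arm difference biased toward zero, are well-founded inferences rather than documented facts.

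The size cannot be computed from the documents. Under the assumed rates with 20 per arm, halving capture takes power from 72% to 25%, from 49% to 17%, or from 45% to 11%. A null result in item 8 would be weak evidence of safety even with full capture, and weaker without it.

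The mismatch between a Safety Monitoring Board and a single appointed officer is a plain inconsistency in the text. Overall this is a cheap improvement worth making, not a flaw that undermines the trial's primary aim.

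**What to change.** - Extend the tracking form in Section 9 (Additional Measures) into a required form, identical in all arms. Collect it once early (for example week 1), at month 1 and at T2. The early contact is a recommendation that follows from the timing in Section 14, since item 7 promises only monthly reports.
- Have it list the effects named in Section 14, an open question on any other event, and medication changes. Staff who are unaware of allocation should collect it.
- State in the Data Safety Monitoring Plan that this form is the source for the monthly reports in item 7 and the comparison in item 8.
- Reconcile the Safety Monitoring Board in item 7 with the appointed Data Safety Monitoring Officer.
- Report event counts by arm with confidence intervals, so that a non-significant test is not read as absence of a difference.

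The cost is a one-page form that existing staff can send by mail or e-mail, with slightly more participant burden. The recorded rate of mild events will rise, and the protocol should say that this is expected.
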